### **Data Analysis:**

A descriptive analysis will be performed on results of each individual question from the mSQAAQ.  All participants having given an informed consent will be included in the analysis population.

The main endpoint of the study will be assessed via mSQAAQ, which is a patient reported outcome (PRO) instrument consisting of 10 individual questions answered on a Likert scale from 1 (Strongly Disagree) to 7 (Strongly Agree). Each question will be analysed and presented individually.

The results of each question will be reported by descriptive statistical analyses on the analysis population. Collected demographic information on study participants will be presented for the total analysis population

as well as any selected sub-populations. A descriptive analysis of any AEs and/or product complaints reported during the study will be included for the total analysis population.

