## 10.3 Data Management & Statistical Analysis

### 10.3.1 Data Analysis

A descriptive analysis will be conducted to assess the ease of use and confidence of use of the lebrikizumab pen. All participants having given an informed consent will be included in the analysis population.

The main endpoint of the study will be assessed via the mSQAAQ. The primary outcome reported from each individual question will be the proportion of participants responding “agreed” or “strongly agreed” to the question. Participants who do not complete an individual item in the mSQAAQ will have their remaining questions analyzed per instrument instructions.

Collected demographic information and health literacy level of study participants will be presented for the total analysis population as well as any selected sub-populations. A descriptive analysis of any AEs and/or product complaints reported during the study will be included for the total analysis population.

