6. GENERAL CONSIDERATIONS

6.1 Sample Size

The planned final sample size of 51 participants with full data is sufficient to provide descriptive insights about the study population. Given the nature of the study it is expected that **cci**%+ of participants enrolled will complete the study and provide full analyzable data.

As defined in the protocol, under the assumption that **cci**% of the participants will respond “agreed” or “strongly agreed” to the device being “easy to use” and “they are confident they can use the device” we will have 95% confidence that the response rate is located in this range of proportions: **cci**% - **cci**%. [Table 1](#) shows a variety of possible sample sizes. For the purpose of the intended claims the 95% CI lower bound should remain above **cci**%, preferably above **cci**%, and the parameters for the calculation of sample size have been selected for that.

Table 1 Sample Size Calculation

Proportion	Margin	Lower CI	Upper CI	Sample Size
95.0%				
95.0%	CCI			
90.0%				
85.0%				
80.0%				

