7. STATISTICAL CONSIDERATIONS

7.1 Statistical Tests and Confidence Intervals

Continuous variables will be summarized using descriptive statistics, i.e., by the number of non-missing and missing observations, mean, standard deviation (SD), first quartile (Q1), median, third quartile (Q3), minimum, and maximum.

Categorical variables will be summarized by frequency counts (n) and percentages (%). Percentages will not include the missing category and are calculated over the number of patients with available (non-missing) data. Counts of missing data will be provided in the tables for information only.

For reporting conventions, percentages will be reported to 1 decimal place unless greater precision is deemed appropriate, except for cases when 100% is presented. In cases of a count of 0, the percentage will not be presented. The 95% confidence interval (CI) for the response rates will be calculated using Clopper-Pearson method.

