7.2 Missing data

Missing data will not be imputed. All analysis will be conducted based on the observed data. Any participants who attend a study visit but do not complete the simulated injection will be excluded from the analysis. Partial completion of the mSQAAQ will be analyzed per the instrument instructions.

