8. OUTPUT PRESENTATIONS

TLFs shells will be developed by IQVIA RWS Biostatistics using the standard processes. The format and content of the statistical analysis is illustrated in the TLF shells provided with this SAP.

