14.1.1 Primary Variables

The SQAAQ is an innovative, 12-item, self-administered questionnaire designed to evaluate the user-friendliness of the device and the patient's confidence during the administration of a subcutaneous injection of a medication. In this study, evaluation of the subject's experience will be based on the mSQAAQ, a self-administered questionnaire that assesses the ease of use and confidence in using the lebrikizumab pen. This tool is comprised of 10 questions (of which 2 questions were removed in the eCRF). Responses are scored on a 7-point Likert scale ranging from 'strongly disagree' to 'strongly agree' as follows:

1 - Strongly disagree

2 - Disagree

3 - Slightly Disagree

4 - Neither agree nor disagree

5 - Slightly agree

6 – Agree*

7 - Strongly agree*

*A combined response of "Agree" or "Strongly agree" will also be presented for all questions.

The following are the questions were removed in the eCRF:

- Question 6: Easy to store device in refrigerator

Document: ELI_LILLY_JAB94256_Auto_inj_SAP_v1.0_03JUN2024

Author: PPD

Version: 2.0

Version date: 16Jul2024

- Question 10: Device is stable against skin during injection

The primary variables are the results reported for each element of the mSQAAQ, which are as follows:

- Question 9: Overall, easy to use
- Question 11: I am confident in my ability to use the device

The other variables are the results reported for each element of the mSQAAQ, which are as follows:

- Question 1: Easy for me to learn how to use
- Question 2: Easy for me to unlock
- Question 3: Easy to hold in my hand when I inject my dose
- Question 4: Easy to inject my dose
- Question 5: Easy to know that my dose is complete
- Question 7: Easy to remove needle shield/cover
- Question 8: Easy to pick up
- Question 12: I am confident my dose is complete

Number, percentage, and 95% confidence interval of partial responders will also provide, overall.

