14.1.2 Analysis of Primary Variables

The primary analysis will be performed on the ENR. Each element will be summarized using descriptive statistics (see [Section 7.1](#)).

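### Does the undefined term 'partial responders' in SAP 14.1.1 leave a planned estimate that cannot be determined?

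*SAP*

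**What the plan says.** After naming Questions 9 and 11 as the primary variables and the other eight questions as further variables, SAP 14.1.1 adds: "Number, percentage, and 95% confidence interval of partial responders will also provide, overall". No definition follows.

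The surrounding text is more specific:

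- **Event.** Protocol 10.3.1: "The primary outcome reported from each individual question will be the proportion of participants responding" 'agreed' or 'strongly agreed'. A note to the scale in SAP 14.1.1 says this combined 6-7 category is shown for every question.
- **Level of reporting.** Protocol synopsis, Data Analysis: "Each question will be analysed and presented individually".
- **Summary and analysis set.** SAP 14.1.2 places the primary analysis on the enrolled set (ENR) and states "Each element will be summarized using descriptive statistics", with a reference to SAP 7.1.
- **Denominator and interval.** SAP 7.1 bases percentages on patients with non-missing data and adds: "The 95% confidence interval (CI) for the response rates will be calculated using Clopper-Pearson method".
- **Incomplete questionnaires.** SAP 7.2: "Partial completion of the mSQAAQ will be analyzed per the instrument instructions". Protocol 10.5 says the same.
- **Table layouts.** SAP 8: "The format and content of the statistical analysis is illustrated in the TLF shells provided with this SAP". The shells are not among the documents available here.

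**The concern.** A percentage with a confidence interval needs an event and a denominator, and this line names neither. At least four meanings are possible:

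- a participant who left some items blank, since 'partial' is used elsewhere only of questionnaire completion;
- a participant who answered 'Slightly agree' (score 5), just below the 6-7 cut;
- a participant who scored 6 or 7 on some but not all ten items;
- a slip for the 6-7 responders themselves.

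The word *overall* could also mean the total sample or a summary across items, and the protocol plans no cross-item summary. If the meaning were chosen after the data were seen, a figure in the primary-variables section would be post hoc. It is also the only sentence in SAP section 14 that names a confidence interval, so one might fear that the interval for the main result depends on it.

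**Working it through.** **1. Does the main result depend on this line?** The chain for Questions 9 and 11 is complete without it: event (Protocol 10.3.1 and the scale note in SAP 14.1.1), analysis set and cross-reference (SAP 14.1.2), denominator and interval method (SAP 7.1). The planning assumption in the protocol synopsis is 95% agreement per question, with 51 analysable participants: 0.95 × 51 = 48.45, nearest count 48. The Clopper-Pearson limits are the 2.5% quantile of Beta(x, n − x + 1) and the 97.5% quantile of Beta(x + 1, n − x). For 48/51 = 94.1% they give 83.8 to 98.8.

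**2. Does the sample size depend on it?** No planning figure is given for partial responders. The margin behind N = 51 is blacked out. An assumed margin of 6 points gives 1.96² × 0.95 × 0.05 / 0.06² = 50.7, rounded up to 51. This is a consistency check only. SAP 6.1 frames the precision ("we will have 95% confidence that the response rate is located in this range of proportions") around the ease-of-use and confidence responses, not around partial responders.

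**3. How far could the line itself move?** Counts marked * are assumed for illustration (56 consented, 53 injected, 51 with complete questionnaires).

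| Reading | Count | Estimate (95% CI) |
|---|---|---|
| At least one item blank, lowest case | 0/51 | 0% (0 to 7.0) |
| At least one item blank, all 56 − 51 = 5 planned non-completers counted | 5/56 | 8.9% (3.0 to 19.6) |
| At least one item blank | 2/53* | 3.8% (0.5 to 13.0) |
| 'Slightly agree' on Question 9 | 3/53* | 5.7% (1.2 to 15.7) |
| 'Slightly agree' on at least one item | 12/53* | 22.6% (12.3 to 36.2) |
| 6-7 on some but not all items, answers independent | 20/51 | 39.2% (25.8 to 53.9) |
| 6-7 on one item (slip) | 48/51 | 94.1% (83.8 to 98.8) |

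The 20/51 comes from 1 − 0.95^10 − 0.05^10 = 0.401, and 0.401 × 51 = 20.5. If each person's ten answers fully agree, that reading gives 0%.

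**4. Which of these does the text support?**

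- The last row repeats an output that SAP 14.1.1 already plans for every question, and the sentence says *also*. If it is a slip, the analyst produces the planned table and nothing is lost.
- The some-but-not-all reading has no wording behind it and sits badly with item-by-item reporting. Its 40% end also needs ten answers from one person to be independent.
- Partial completion is the only reading that matches the documents' own use of 'partial'. Its range is 0% to 8.9%, and both ends are extremes: SAP 6.1 describes the 51 as having full data, so 0/51 holds by construction, while 5/56 treats every planned non-completer as a partial completer.
- *Overall* has a plain meaning, because SAP 7.3 plans subgroup summaries: the total sample.

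**5. Is the denominator open?** SAP 7.1 counts patients. Pooling answers (480/510 = 94.1%, 91.7 to 96.0, width 4.3 points against 15.0) would give an interval that is too narrow, but the SAP does not call for pooling. Among participant denominators the choice matters little: an assumed 15 events give 15/51 = 29.4% and 15/56 = 26.8%, a difference of 2.6 points.

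**The case for a change.** The strongest case for a change is that correcting the grammar does not supply the event. A reader cannot program this line from the SAP alone, and the defaults do not fully rescue it. If the event is an incomplete questionnaire, a non-missing rule applied carelessly would drop the people being counted. The ENR also sits uneasily with the exclusions in SAP 7.2 and Protocol 10.5, which themselves differ. SAP 6.1 speaks of intended claims that rest on a lower confidence limit, and clarifying the line would take one sentence.

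Part of this stands. The term is undefined in the visible text, and the event, not the denominator, is the main gap. The rest carries less weight. Once the variable is named as complete or incomplete, that status is known for everyone who was given the questionnaire, so a non-missing rule need not remove anyone. The tension between the ENR and the exclusions is a general matter that this line does not create. The lower-limit target concerns the ease-of-use and confidence rates, which this line does not touch. That the clarification is cheap does not show that the plan goes wrong without it.

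**Conclusion.** No change to the plan follows. SAP 14.1.1 contains one unclear, ungrammatical sentence about an auxiliary output, which is missing detail and not a faulty analysis. Under the best-supported reading the line would show a small count of incomplete questionnaires, between 0% and 8.9% at the planned numbers. Under the slip reading it repeats a table already planned. Under every reading the 6-7 proportions for Questions 9 and 11 and their intervals are the same. The study is descriptive, plans no comparisons, and ties no stated decision to this figure.

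The conclusion assumes that analysts follow SAP 7.1 and 14.1.2 as written, with participants as the unit, and that the meaning is fixed in the table shells or by a routine query before the output is run. The shells could not be checked here. If they are silent too, the line should be read with caution, but the study's main results would stand.

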14.1.2 Analysis of Primary Variables

The primary analysis will be performed on the ENR. Each element will be summarized using descriptive statistics (see [Section 7.1](#)).

15. SAFETY OUTCOMES

All outputs for safety outcomes will be based on the ENR. AE/SAE/Product complaints will be coded using the latest version of MedDRA at the time of data analysis. The MedDRA version used for a given output will be added in the footnote.

A listing by patient including each verbatim term, preferred term, start and end date, ongoing status (Yes/No), action taken, outcome, severity, seriousness, relationship to the device, and relationship to drug will also be provided.

A listing of adverse events, medications and product complaints will be provided. It will include patient responses to whether the participant experienced any adverse events during this study, whether the participant is currently taking any medication or therapy, whether the participant identified any product complaints, and whether a product complaint form was submitted to the study sponsor.

